8. Eligibility criteria were organized for ease of use and updated based on Investigator feedback to allow enrollment of patients with Grade 2 hypophosphatemia due to prior cancer treatment (if receiving appropriate replacement therapy), Grade 2 hypothyroidism (if on stable replacement doses), Grade 2 lymphopenia, and Gilbert's syndrome. Laboratory criteria for hematology must be met with adequate washout from growth factors / transfusions. Laboratory criteria for electrolytes were removed. Washout for prior antibiotics reduced to 2 weeks prior to first dose (versus before start of Screening). Prior treatment requirements for Phase I were clarified. Washout for prior anti-cancer therapy clarified as for disease under study. Exclusion for patients with prior hypersensitivity to other biologic drugs or monoclonal antibodies was removed.
9. DLT criteria for Grade 3 liver function test elevations were adjusted to apply stricter criteria for high Grade 3 elevations while allowing more time for low Grade 3 elevations to resolve. DLT criteria for concurrent ALT/AST and bilirubin increases were aligned with Potential Hy's Law criteria. DLT criteria regarding amylase / lipase increase were added. DLT criteria for hypotension was modified to align with CRS treatment guidelines (vasopressor use does not automatically trigger DLT). The Sponsor must be notified within 24 hours of any serious adverse event (SAE), DLT, \geq Grade 2 cytokine

release syndrome (CRS), or \geq Grade 3 hepatic function abnormality (rather than notified immediately for any unexpected \geq Grade 3 AE).

10. Allowed/prohibited concomitant medications was edited to provide more flexibility in modifying ongoing hypertensive medications, in cases where withholding anti-hypertensive medications is contraindicated, allow the monoclonal antibody denosumab (as supportive care for patients with bone metastasis), clarify that prohibition of anti-cancer therapies refers to systemic therapies for the cancer under study (eg, adjuvant tamoxifen for prior breast cancer would not be prohibited), allow corticosteroids for known allergy to contrast reagents, and allow SST to recommend pre-medication based on the emerging safety profile.

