5.3 Exclusion Criteria

Patients with any of the following will not be included in the study:

Disease Under Study and Prior Anti-Cancer Treatment

1. Presence of symptomatic or untreated central nervous system (CNS) metastases, leptomeningeal disease, cord compression, or CNS metastases that require doses of corticosteroids within 3 weeks prior to the planned first administration of study drug.
NOTE: Asymptomatic and adequately treated CNS metastases are not exclusionary provided the patient is neurologically stable

2. Systemic anti-cancer therapy for the disease under study within 2 weeks of the planned first administration of study treatment. For cytotoxic or immunotherapy agents that can present with major delayed toxicity (eg, anti-CTLA-4), a 4-week washout period is required
3. Radiotherapy within 2 weeks of the planned first administration of study drug. **NOTE:** palliative radiotherapy to a limited field, such as for the treatment of bone pain or a focally painful tumor mass, is not exclusionary
4. Presence of National Cancer Institute Common Terminology Criteria for Adverse Events (NCI CTCAE) \geq Grade 2 toxicity due to prior cancer therapy (except Grade 2 alopecia, stable Grade 2 peripheral neuropathy, Grade 2 endocrine disorder [on stable replacement doses and without symptoms], Grade 2 hypophosphatemia [on appropriate replacement therapy] and Grade 2 ototoxicity)

Laboratory Parameters

5. Patient with any out-of-range laboratory values defined as shown below. Hematology evaluations must be performed \geq 7 days after any blood or blood product transfusion and \geq 14 days after any dose of hematologic growth factor.
 - Creatinine clearance (calculated using Cockcroft-Gault formula or measured) < 40 mL/min
 - Total bilirubin $> 1.5 \times$ upper limit of normal (ULN); **NOTE:** for patients with Gilbert's syndrome; exclude if total bilirubin $> 3.0 \times$ ULN or direct bilirubin $> 1.5 \times$ ULN
 - Alanine aminotransferase (ALT) $> 3 \times$ ULN
 - Aspartate aminotransferase (AST) $> 3 \times$ ULN
 - Absolute neutrophil count (ANC) $< 1.0 \times 10^9/L$
 - Absolute lymphocyte count $< 0.5 \times 10^9/L$
 - Platelet count $< 75 \times 10^9/L$
 - Hemoglobin < 8 g/dL

Medical History and Concomitant Medications

6. Any active manifestations of autoimmune disease of the skin, including psoriasis and scleroderma, or history of severe skin manifestation of graft versus host disease

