Hepatic and pancreatic	Grade ≥ 2 elevated total bilirubin ($> 2 \times$ ULN) with concurrent Grade ≥ 2 elevated ALT and/or AST ($> 3 \times$ ULN), with no clear alternate etiology (eg, biliary obstruction with elevated alkaline phosphatase), is a DLT Grade 3 isolated ALT and/or AST ($> 5-8 \times$ ULN) elevation or Grade 3 isolated bilirubin elevation ($> 3-5 \times$ ULN) that does not resolve to \leq Grade 1 within 14 days of onset is a DLT \geq Grade 3 isolated ALT and/or AST ($> 8 \times$ ULN) elevation or \geq Grade 3 isolated bilirubin ($> 5 \times$ ULN) elevation is a DLT \geq Grade 3 amylase and/or lipase elevation, with associated clinical signs, symptoms, or radiographic evidence of pancreatitis, is a DLT
Gastrointestinal	Grade 3 nausea, vomiting or diarrhea persisting for > 3 days after onset, despite optimal therapy, is a DLT
Hypotension	Grade 3 hypotension that does not resolve to \leq Grade 1 within 6 hours of onset, despite optimal therapy, is a DLT Grade 4 hypotension of any duration and with any management is a DLT
Hypertension	Grade 3 hypertension (systolic BP ≥ 160 mm Hg or diastolic BP ≥ 100 mm Hg) persisting > 2 days after onset, despite treatment, is a DLT Grade 4 hypertension of any duration is a DLT
Infection	Grade 3 infection or fever in the absence of neutropenia that persists > 7 days after onset is a DLT Grade 4 infection of any duration is a DLT

DLTs include \geq Grade 3 AE occurring during the DLT evaluation period, with a suspected relationship to study drug, with the following modifications:	
Tumor Flare	Grade 3 inflammatory reaction at a tumor site associated with local anti-tumor immune response that does not resolve to \leq Grade 2 within 7 days after onset is a DLT
Electrolyte Abnormalities	Grade 3 electrolyte abnormalities that do not resolve to \leq Grade 1 within 3 days after onset, despite optimal medical management, are DLTs Grade 4 electrolyte abnormality of any duration is a DLT
Skin toxicity	Grade 3 rash and/or pruritis that persists $>$ 7 days after onset, despite optimal medical management, is a DLT Grade 4 cutaneous toxicity of any duration is a DLT
Fatigue	\geq Grade 3 fatigue that persists $>$ 4 days after onset is a DLT
Infusion-related reaction / hypersensitivity / anaphylaxis	Grade 3 infusion-related reaction that does not resolve to \leq Grade 1 within 6 hours of onset, despite appropriate medical management, is a DLT Grade 4 infusion reaction is a DLT

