Grade 3	
Notify the Sponsor within 24 hours.
 
As above for Grade 2; additionally, consider further testing to assess liver synthetic function and consider hepatology consult to advise on management and additional workup. Consider IV corticosteroid therapy (eg, hydrocortisone 100 mg or equivalent) per institutional guidelines if not resolving within 48 to 72 hours.
	
Do not administer IMCnyeso until LFTs have improved to \leq Grade 1 and following discussion and agreement with the Sponsor Medical Monitor.
 
 For isolated ALT and/or AST elevation ($>5-8 \times$ ULN) or isolated total bilirubin elevation ($>3-5 \times$ ULN) that resolves to Grade ≤ 1 within 7 days, dosing at the current dose level may resume For isolated ALT and/or AST elevation ($>5-8 \times$ ULN) or isolated total bilirubin elevation ($>3-5 \times$ ULN) that requires > 7 days to resolve, dosing may resume with ≥ 1 dose-level reduction in IMCnyeso For isolated ALT and/or AST elevation ($>8 \times$ ULN) or isolated total bilirubin elevation ($>5 \times$ ULN) that resolves to Grade ≤ 1, dosing should be permanently discontinued unless the Investigator believes the overall benefit-risk favors continued treatment, in which case dosing may resume with ≥ 1 dose-level reduction in IMCnyeso
Grade 4	
As above for Grade 3; additionally, promptly consider IV corticosteroid therapy (eg, hydrocortisone 100 mg or equivalent) per institutional guidelines if not resolving within 24 hours. Perform supplementary testing to assess liver synthetic function and obtain hepatology consult to advise on management and additional workup.
	
Study medication must be permanently discontinued.

Grade	Recommended Toxicity Management	Dose Modifications
Vomiting		
Grade 2	Anti-emetic therapy as per institutional standard. IV fluids, electrolyte supplementation, and other supportive measures for additional adverse events as needed.	May continue dosing.

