Section 5.3	Allow patients with Grade 2 hypophosphatemia [if receiving appropriate replacement therapy] or hypothyroidism [if on stable replacement doses] due to prior cancer therapy to enroll	Hypophosphatemia due to prior ifosfamide and hypothyroidism due to prior checkpoint inhibitors are relatively common in the eligible patient population and are not expected to be exacerbated by IMCnyeso treatment

Section in Amendment 1	Change	Rationale
Section 5.3	Patients with leptomeningeal disease or cord compression are not eligible for study participation	To ensure adequate baseline health status of enrolled patients
Section 5.3	Clarify that hematology evaluations used to determine study eligibility must be performed \geq 7 days from any blood or blood product transfusion and \geq 14 days from any dose of hematologic growth factor; removed exclusion criteria regarding use of hematopoietic growth factors and erythroid stimulating agents	To ensure that enrolled patients have adequate hematologic function and simplify the protocol
Section 5.3	Eligibility criteria for renal function will be based only on creatinine clearance, rather than creatinine concentration and/or creatinine clearance	To reduce ambiguity in eligibility criteria
Section 5.3	Added for patients with Gilbert's syndrome exclude if total bilirubin $> 3.0 \times$ ULN or direct bilirubin $> 1.5 \times$ ULN	Slightly elevated bilirubin in patients with Gilbert's syndrome is not a safety concern for IMCnyeso
Section 5.3	Reduced minimum absolute lymphocyte count needed for eligibility to $<0.5 \times 10^9/L$ (previously $1.0 \times 10^9/L$)	Grade 2 lymphopenia is a relatively common finding in patients with advanced cancers and is not expected to impact the safety or efficacy of IMCnyeso
Section 5.3	Removed electrolyte lab abnormalities from exclusion criteria	Electrolyte abnormalities can be appropriately managed and should not be exclusionary
Section 5.3	Removed exclusion criterion for prior hypersensitivity to other biologic drugs or monoclonal antibodies	Prior hypersensitivity to another biologic drug does not necessarily indicate elevated risk of hypersensitivity to IMCnyeso
Section 5.3	Systemic antibiotics must be completed at least 14 days prior to the first dose of study drug (rather than prior to screening)	To improve operational feasibility while maintaining appropriate safeguards

Section in Amendment 1	Change	Rationale

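### Table 6-3 requires recovery to Grade 1 or lower although eligibility admits two Grade 2 baselines, so a confirmed, related Grade 3 event that returns fully to the entry level is scored as a DLT

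*Protocol*

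**What the plan says.** **Eligibility (Protocol Section 5.3).** Exclusion criterion 4 bars toxicity of Grade 2 or worse left over from earlier cancer treatment, with listed exceptions that include "Grade 2 hypophosphatemia [on appropriate replacement therapy] and Grade 2 ototoxicity". Criterion 5 gives laboratory limits. No electrolyte is among them, and the Global Amendment 2 summary records the change: "Laboratory criteria for electrolytes were removed". Total bilirubin is limited to 1.5 × ULN, but "for patients with Gilbert's syndrome; exclude if total bilirubin" is above 3.0 × ULN or direct bilirubin is above 1.5 × ULN.

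**DLT scoring (Protocol Section 6.12, Table 6-3).** The electrolyte row covers "Grade 3 electrolyte abnormalities that do not resolve to" ≤ "Grade 1 within 3 days after onset, despite optimal medical management, are DLTs". In the hepatic row, a Grade 3 isolated bilirubin rise (> 3–5 × ULN) that does not settle to ≤ "Grade 1 within 14 days of onset is a DLT". SAP Section 8.1 refers back to Section 6.12 and adds nothing on baseline.

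**Rationale (Protocol Section 13.5.2).** The reason given for the phosphate exception is that "Hypophosphatemia due to prior ifosfamide and hypothyroidism due to prior checkpoint inhibitors are relatively common in the eligible patient population". The same sentence goes on to say that treatment is not expected to make these conditions worse.

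**Resumption of dosing (Table 6-4, Grade 3 hepatic).** "Do not administer IMCnyeso until LFTs have improved to" Grade 1 or lower, and the Medical Monitor has agreed.

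**The concern.** A DLT should reflect what the drug did after the first dose. For a patient who enters at Grade 2, these two rows ask for something else: recovery to a better state than the one in which the patient was admitted. A full return to the entry level does not count as resolution.

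The incidence of DLTs is a Phase I primary endpoint and the only outcome that the BLRM uses, so an event scored this way carries the same weight as any other DLT. Events meeting the DLT definition also feed the Phase II trigger in Section 6.11 (a rate above 30% after at least 12 subjects), although that trigger only convenes a safety teleconference.

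**Working it through.** No sample size, power or error rate has to be reproduced. The check sets the rules side by side.

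1. **Bilirubin grades on the protocol's own labels.** Table 6-3 labels total bilirubin > 2 × ULN as Grade 2 or higher and starts Grade 3 at > 3 × ULN. An admitted Gilbert's baseline between 2 and 3 × ULN is therefore Grade 2. If the Grade 1/2 cut is assumed to be as low as 1.5 × ULN, more Gilbert's baselines are Grade 2 and the conclusion is unchanged.

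2. **Search for a baseline allowance.** Section 6.12, the definition of DLT-evaluable patients in Section 6.10.2 and SAP Section 8.1 contain none.

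3. **Confirmation.** Section 6.12 requires a re-test at least 24 hours later when there are no clinically significant signs or symptoms. I read this as requiring the value to be still Grade 3 at the re-test.

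4. **Cases, each judged at least possibly related** (the bilirubin values are illustrative):

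| Entry | Event | Course | Scored |
|---|---|---|---|
| Phosphate Grade 2 | Grade 3, confirmed or symptomatic | Grade 2 by day 3 | DLT: never ≤ Grade 1 |
| Gilbert's, 2.5 × ULN | 3.2 × ULN isolated, confirmed or symptomatic | 2.5 × ULN by day 14 | DLT: never ≤ Grade 1 |
| Phosphate Grade 2 | Grade 3, no symptoms | Grade 2 at re-test | Not confirmed, so not a DLT |
| No Gilbert's, ≤ 1.5 × ULN | > 3–5 × ULN isolated, confirmed | Entry level by day 14 | Not a DLT: entry is at most Grade 1 |

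5. **What is not affected.** ALT and AST entry is capped at 3 × ULN and Table 6-3 labels > 3 × ULN as Grade 2 or higher, so no conflict is shown there. Bilirubin > 5 × ULN and Grade 4 electrolyte events are DLTs whatever the recovery.

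6. **Weight of one event.** One DLT is 1/3 = 33% of a cohort of 3, or 1/6 = 17% of a cohort of 6. In the protocol's sample paths, 0/3 at 30 mcg is followed by 100 mcg (Table 13-9). In the path with 1/3 at 30 mcg, the next cohort treated is at 25 mcg (Table 13-10, although that row prints 100 as the recommendation). Any single DLT has this weight, so it does not measure this defect. I give no BLRM shift of my own: a rebuild from Table 13-6 and the six pseudo-patients of Table 13-7 did not reproduce Table 13-8 (mean DLT probability 0.166 against 0.109 at 3 mcg, and 0.252 against 0.297 at 100 mcg).

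**The case against.** **The re-test filters transient values.** This stands in part. A reader might infer that any brief dip to Grade 3 becomes a DLT. The documents do not support that: without symptoms, a value back at Grade 2 the next day would normally fail confirmation. The re-test does not help once Grade 3 is confirmed or symptomatic.

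**Attribution filters the rest.** Section 6.12 requires both a suspected drug relationship and no link to disease, inter-current illness or concomitant medication, so a Gilbert's fluctuation may be attributed elsewhere. This narrows the problem, but it is a case-by-case judgement and not a baseline rule. Section 8.4 counts possibly related events as related even where a link is thought improbable, and reserves the unrelated category for certainty. The row for concurrent transaminase and bilirubin rises has an alternative-cause clause; the two rows at issue do not. Section 6.12 lets the SST add DLTs and states no power to remove an event that meets Table 6-3.

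**Entry is not as open as it looks.** A reader might infer from criterion 5 that no electrolyte abnormality is excluded. Criterion 4 still excludes Grade 2 or worse electrolyte toxicity from prior cancer therapy, and hypophosphatemia on replacement is its only electrolyte exception.

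**The DLT definitions are meant to be conservative.** The synopsis says so. That supports strict scoring of drug effects; it does not explain why a patient's admitted starting grade should decide the outcome.

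**Conclusion.** The conflict is in the text and holds within narrow limits. It needs an admitted Grade 2 baseline (hypophosphatemia on replacement, or Gilbert's syndrome with bilirubin in the Grade 2 range), a Grade 3 value that is symptomatic or confirmed, a judgement of at least possible relatedness, and recovery to the entry level but no further. When all of these occur, the protocol scores a DLT although the patient is back where eligibility admitted them.

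No magnitude is claimed. The documents give neither the share of such patients nor their rate of Grade 3 events, and the statement that hypophosphatemia is relatively common comes with the expectation that treatment will not worsen it. A reader might build a rate from an assumed share. At 10% to 20%, the chance that a cohort of 3 contains such a patient is 1 − 0.90³ = 27% to 1 − 0.80³ = 49%. That counts cohorts with an exposed patient, not wrongly scored DLTs.

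A reader might also infer that escalation has already been distorted. The documents do not show this: Protocol Section 1.4 reports no DLT in 15 patients as of 22 January 2020, and SAP Table 1 shows escalation continuing to a planned 30-100-300 mcg cohort.

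The point still deserves correction, because it can misclassify a primary endpoint and the remedy uses data already collected.

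**What to change.** In the electrolyte and isolated-bilirubin rows of Table 6-3, state that for the DLT endpoint resolution is scored against the patient's baseline grade where the admitted baseline is above Grade 1, so that a return to baseline within the existing window is not a DLT. Use the baseline definition in Section 9.1. The chemistry panel, which includes phosphate and total bilirubin (Table 7-6), is already taken at Screening and on C1D1. Section 6.16 also uses Table 6-3 to define unacceptable toxicity, so word the change as an endpoint-scoring rule and leave its bearing on discontinuation to the sponsor.

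Apply the wording to cohorts already scored, so that the BLRM does not mix two definitions. SAP Table 1 lists 4 + 3 + 5 + 3 + 5 + 4 = 24 patients enrolled in cohorts 1 to 6. The change can only remove DLTs, so only patients scored as having one need review. For the first 15 patients none had been reported at the January 2020 cut-off, although those data were not fully validated.

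The cost is an amendment and that check. SAP Section 8.1 follows Section 6.12 and needs only the updated protocol version.

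Separately, the sponsor must reconcile the Grade 1 condition for resuming treatment in Table 6-4 (Grade 3 hepatic) with the Gilbert's limit in Section 5.3, because a patient admitted at Grade 2 may never meet it. No clinical threshold is proposed here.

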6.13 Concomitant Therapy

6.13.1 Permitted Concomitant Therapy

In general, concomitant medications and therapies deemed necessary for the supportive care and safety of the patient are allowed. Examples include anti-diarrheal medications, anti-emetics, electrolyte supplementation, intravenous fluids, hematologic growth factors, or blood transfusions. However, hematologic growth factors and blood transfusions should only be administered starting with Cycle 2 to avoid confounding interpretation of potential drug-related toxicities during the DLT evaluation period.

Patients are required to notify the investigational site staff about any new medications, herbal remedies, or dietary supplements taken after the start of the study treatment, regardless of treatment duration. All concomitant medications and significant non-drug therapies (including physical therapy, herbal or natural medications and blood transfusions) administered during the study must be listed on the Concomitant Medications Log or the Surgical and Medical Procedures log in the eCRF.

IV hydration required to manage toxicity associated with the study medications (eg, hypotension) should be recorded in the Concomitant Medications Log in the eCRF.

Palliative radiation therapy to non-target lesions is permitted during the study after consultation with the Sponsor Medical Monitor and should be recorded in the eCRF as concomitant therapy.

6.13.2 Concomitant Therapy Requiring Caution

Anti-coagulant therapy is permitted. International normalized ratio should be monitored as clinically indicated per the Investigator's discretion. Ongoing anti-coagulant therapy should be temporarily discontinued to allow tumor biopsy according to institutional guidelines. Recent hospitalizations that required low dose heparin for deep vein thrombosis prophylaxis are not a contraindication.

Anti-hypertensive drugs are allowed as concomitant medications; however, because transient hypotension has occurred during infusions of monoclonal antibodies, anti-hypertensives should not be administered 24 hours before and 24 hours after IMCnyeso administration in the first 6 weeks of treatment. Thereafter, anti-hypertensives can be reintroduced at the discretion of the Principal Investigator. Appropriate management of patients with more severe hypertension, receiving medications that may cause rebound hypertension when abruptly discontinued, or on multiple blood pressure medications, should be discussed with the Sponsor Medical Monitor prior to making any adjustments during the first 6 weeks of treatment.

Non-live vaccines are allowed but are not to be administered within 14 days before, and 28 days after, the first dose of IMCnyeso. Following completion of the first treatment cycle, non-live vaccines should not be given within 24 hours before or after IMCnyeso administration.

6.13.3 Prohibited Concomitant Therapy

During study treatment, patients may not receive other investigational drugs, agents, devices, chemotherapy, or any other systemic therapies that may be active against the cancer under study.

Additionally, no other therapeutic monoclonal antibodies (excepting denosumab) and no immunosuppressive medication may be administered to patients in this study (except as noted in [Exclusion Criterion 11](#) and [Section 6.15](#)).

While systemic corticosteroid therapy may interfere with the mechanism of action of the study medications, its use is permitted/recommended in the following settings:

- Pre-medication for known allergy to contrast reagents
- To manage toxicities (eg, infusion reactions, hypotension not resolving with fluid support) as noted in [Section 6.15](#)

- Replacement-dose steroids (ie, prednisone \leq 10 mg QD or equivalent) in the setting of adrenal insufficiency (patients with a pre-existing history of adrenal crisis are excluded from study participation; see [Exclusion Criterion 11](#))
- Based on the emerging safety profile of IMCnyeso, the SST may decide to recommend a standard pre-treatment regimen (which may include antihistamine, acetaminophen, and/or corticosteroid)

Any additional uses of systemic corticosteroid therapy during the study should be discussed with the Sponsor Medical Monitor.

Live or attenuated vaccines are prohibited from 28 days prior to the first dose of IMCnyeso until 30 days after the last dose of IMCnyeso.

